8.9 Continued provision of the intervention for participants (if appropriate)

After the study, participants will be returned to the care of the weight management services where the local PI can make recommendations as to the continuation of the study treatment dependent on tolerance or side-effects (where applicable with regards to drug availability and local prescribing guidelines). Participants will be informed about the recommendation. For example, that they have been recommended to continue LIRA 3mg, but it will also be stressed that this will be down to the discretion of the GP and local prescribing guidelines.

8.10 Response to the COVID19 global pandemic (Urgent Safety Measure)

During the COVID19 global pandemic, a thorough risk assessment was conducted, and as a result the following appropriate adaptations have been made to the delivery of the study:

- Face to face study visits may be replaced with virtual consultations via telephone call or video call via the MyClinic application. Verbal consent will be sought from participants in advance of the video consultation (via MyClinic) and will be documented in the medical records. Face to face visits may continue at sites if this is in accordance with the local trust policy and appropriate risk mitigations are implemented at site to reduce the risk to participants. Risk and mitigations will be detailed in the risk assessment. During this period both face to face visits and virtual ones may be conducted in line with the USM adaptations detailed below.
- Participants due a V11 (study primary endpoint) are asked to weigh themselves at home on scales provided by the study team. A working instruction has been provided to participants to support them to record their weight in a standardised manner. During virtual consultations, the study nurse or doctor may witness the weight measurement process (following receipt of verbal consent from the participant). In the absence of consent from the participant, the participant will report the weight measurement verbally and follow this up with a photo of the weight value (source data).
- A courier service has been arranged for study drug deliveries to participants; some sites are using a drop off/collection service either on site or to participant's homes. Participants on the Liraglutide arm will attend a virtual consultation and weigh themselves prior to additional study drug being dispensed.
- Participants in the Liraglutide arm who are of child bearing potential will receive a pregnancy test prior to their visit (to be used on the day of the visit) and the result reported either verbally to the study team during the video call or via a photo (source data) following a telephone call.
- The study quality of life questionnaire packs (HSRUQ, TSQM, EQ-5D, IWQOL-Lite, IPAQ-Long and PHQ-9) will be mailed to participants, where applicable, to be completed at home and returned to the study team via the postal system.

As a result of conducting virtual consultations and telephone calls, the following procedures will not be performed during the COVID19 pandemic, therefore have been halted as an urgent safety measure:

- BP and Pulse measurements – Participants who are known to have hypertension have home BP monitoring machines and their BP measurements are being collected and assessed by the study team during remote visits. There is no undue risk for those who do not have hypertension, as Liraglutide is not related to BP, and participants are all established on the drug.
- Bloods (lipids, renal, LFTs, thyroid, FBC & HbA1c, amylase) at V9, 11 & 13/15 only - The amylase test usually taken at visits 9, 11 & 15 is a safety blood in relation to pancreatitis. During the remote visits, all participants will be monitored for any new symptoms which will be appropriately managed by the study clinical team. The small number of participants who have diabetes will regularly check their blood glucose at home as usual. All other bloods are taken to assess efficacy, therefore not conducting them will have no impact on participant safety. All participants will be asked to report AE/SAE during remote visits.
- ACR urine test – Not conducting this poses no additional risk to participants.

Once restrictions due to the COVID19 pandemic have been lifted, a further risk assessment will be completed and in agreement with the Sponsor, Study team and NHS Host Organisations, face to face visits will be re-implemented. For the avoidance of doubt, virtual consultations will still be an option for study visits, as preferred by the participant or recommended by the study clinician, to aid the retention of participants and study visit attendance and collection of primary outcome data (via self-reported weight measurement data).

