8.3.1 Baseline Visit (Day 0) – All Participants

Only those patients who are eligible based on the data collected at the Screening and Consent Visit will proceed to the Baseline Visit (Day 0). Weight, waist circumference, blood pressure and pulse rate will be recorded for all the patients in line with study SOPs. The patient will also complete questionnaires to provide demographic and medical history details and additional data will be collected as indicated in Appendix 3 (e.g. self-reported physical activity using the International Physical Activity Questionnaire). Serious Adverse Event (SAE) and Adverse Event (AE) recording and documentation of changes in medication or diseases will be performed. Randomisation will be

performed and participants will be informed of their group allocation (see Randomisation Section 8.3.1.1 below). Participants in both groups (standard care [control group] vs. standard care + LIRA 3mg [targeted prescribing pathway]) will be counselled about the study visits and what they can realistically expect with each treatment option. Participants allocated to the targeted prescribing pathway will receive injection training, storage and dispensing. All participants will be informed that they may contact their GP or the study team at any time.

Urine pregnancy tests will be performed for females of childbearing potential. Additional testing will also occur at any time during the trial if a menstrual period is missed or as required by local law. The test will be performed at the study site. Pregnancy testing will not be required for women who have undergone a hysterectomy or bilateral tubal ligation, or for women above the age of 50 years old, who have been without menses for at least 1 year. Participants will be given clear instructions regarding contraception throughout the study. Adequate contraceptive measures have been defined as sterilisation, intra-uterine device, oral contraceptives, consistent use of barrier methods, male sterilisation or true abstinence (when this is in line with the preferred and usual lifestyle of the participant) (www.hma.eu/fileadmin/dateien/Human_Medicines/01-About_HMA/Working_Groups/CTFG/2014_09_HMA_CTFG_Contraception.pdf – accessed 21/07/2017).

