Adherence with other anti-obesity medications [#]								X		X	X				X
Adherence to Tier 3 (or equivalent) Service			X	X	X	X	X	X	X	X	X	X	X	X	X
Contacts with GP/HCP		X	X	X	X	X	X	X	X	X	X	X	X	X	X
Inpatient and Outpatient apt's		X	X	X	X	X	X	X	X	X	X	X	X	X	X
Medications cost		X									X				X
QUESTIONNAIRES^{^^^}															
HSRUQ		X									X				X
TSQM###		X									X				X
EQ-5D		X									X				X
IWQOL-Lite		X									X				X
IPAQ-Long		X									X				X
PHQ-9		X									X				X

*Only for participants at the LIRA 3mg group who are on active treatment

^{§§}Target dose by week 8. ^{§§}Optional Telephone calls to check tolerance and up-titrate at weeks 1, 3 & 5.

**As required for participants with identified risk OSA or current OSA based on CPAP use and type of CPAP (variable or fixed pressures CPAP)

*** Only for prediabetic, diabetic and hypertensive individuals

****Where possible the week 52 visit should continue to be scheduled within the (± 14 days) study visit window, however to aid retention

and to help maximise data collection for the study primary end point, the week 52 visit window can be extended to ± 3 months.

Only for participants in the standard care group on treatment with anti-obesity drugs

#[#] Only for participants with diagnosis of T2DM

#^{##} For participants on treatment either with LIRA 3mg or other anti-obesity medication

[^] Only participants who report problems with injection and/or side-effects may be reviewed by study clinician

^{^^} A repeat screening visit may take place to assess eligibility

Drug dispensing unscheduled visits may occur at any point within the study period for participants in LIRA3 mg group as required (not depicted above)

^{^^^}In response to the COVID19 global pandemic, an interim time point for the quality of life questionnaires has been added (HSRUQ, TSQM, EQ-5D, IWQOL-Lite, IPAQ-Long and PHQ-9). These will be sent out to all participants during the COVID19 pandemic.

^{^^^^} These activities will not be completed during the COVID19 pandemic restriction period, however once restrictions are lifted participants that resume face to face visits will be completed as per the original protocol.

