2.2 Secondary Endpoints

2.2.1 Definition and Derivation of Secondary Endpoints

Endpoint	Time point (weeks)	Endpoint derivation
Anthropometric endpoint		
Absolute change in weight (kg) from baseline	16, 32, 52, 104	Follow-up weight – baseline weight
Relative change in weight (%) from baseline	16, 32, 52, 104	(Baseline weight – follow-up weight)/baseline weight * 100
Weight loss of $\geq 5\%$, $\geq 10\%$ and $\geq 15\%$	16, 32, 52, 104	Binary indicator of 1 if relative change in weight from baseline is $\geq 5\%$ loss (or $\geq 10\%$ or $\geq 15\%$, respectively), 0 otherwise
Maintenance of weight loss of $\geq 15\%$ among those who lost $\geq 15\%$ at 52 weeks	104	Binary indicator of 1 if relative change in weight from baseline is $\geq 15\%$ loss, 0 otherwise, only calculated for those who lost $\geq 15\%$ of baseline weight at 52 weeks.
Absolute change in BMI (kg/m^2) from baseline	52, 104	Follow-up BMI – baseline BMI
Absolute change in waist circumference (cm) from baseline	52, 104	Follow-up waist circumference – baseline waist circumference
Obesity-related co-morbidities and their treatments (General)		
Score on King's College Obesity Staging System assessment	52, 104	Scored as per Staging System (Appendix 1) as Stage 0 (normal health), 1 (at risk of disease), 2 (established disease), 3 (advanced disease) with baseline values also presented
Quality of life (EQ5D) – Descriptive System	52, 104	Scored as per https://www.unmc.edu/centric/_documents/EQ-5D-5L.pdf with change from baseline value analysed separately for each dimension
Quality of life (EQ5D) – Visual Analogue Scale	52, 104	Scored as per https://www.unmc.edu/centric/_documents/EQ-5D-5L.pdf with change from baseline value analysed
Impact of Weight on Quality of Life-Lite (IWQOL-Lite)	52, 104	Transformed total score on scale of 0-100 scored as per https://www.qualityoflifeconsulting.com/iwgol-lite.html with change from baseline

		value analysed
Patient Health Questionnaire-9 (PHQ-9)	52, 104	Scored as per Appendix 2 as minimal depression, mild depression, moderate depression, moderately severe depression, severe depression with baseline values also presented
Patient Health Questionnaire-9 (PHQ-9)	52, 104	Total score generated as per Appendix 2 with change from baseline analysed
Obesity-related co-morbidities and their treatments (Obstructive Sleep Apnoea; OSA)		

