Proportion of those with diabetes at baseline with HbA1C<6.5%	52, 104	From HbA1c measurement, a binary indicator will be derived, being 1 if participant achieves the target and 0 if they do not.
Change in Albumin-Creatinine Ratio (ACR; mg/mmol) from baseline for participants with diabetes, prediabetes, or hypertension	52, 104	Follow-up ACR – baseline ACR, only for participants defined as having diabetes, prediabetes, or hypertension
Obesity-related co-morbidities and their treatments (Hypertension)		

Systolic blood pressure (mmHg)^b	52, 104	Follow-up systolic blood pressure – baseline systolic blood pressure
Diastolic blood pressure (mmHg)^b	52, 104	Follow-up diastolic blood pressure – baseline diastolic blood pressure
Hypertension	52, 104	Binary indicator of 1 if participant is on antihypertensive medications or systolic blood pressure > 140 mmHg ^c , 0 otherwise with baseline values also presented
Number of agents for hypertension	52, 104	Change from baseline in total number of medications taken for hypertension defined as medications in any of the following classes: ACE-inhibitors, calcium channel blockers, thiazide diuretics, alpha-blockers, and beta-blockers.
Obesity-related co-morbidities and their treatments (Dyslipidaemia)		
LDL cholesterol (mmol/L)	52, 104	Follow-up LDL cholesterol – baseline LDL cholesterol
HDL cholesterol (mmol/L)	52, 104	Follow-up HDL cholesterol – baseline HDL cholesterol
Total cholesterol (mmol/L)	52, 104	Follow-up total cholesterol – baseline total cholesterol
Triglycerides (mmol/L)	52, 104	Follow-up triglycerides – baseline triglycerides
Number of agents for dyslipidaemia	52, 104	Change from baseline in total number of medications taken for dyslipidaemia defined as medications in any of the following classes: statins, fibrates, and ezetimibe.
Number of participants referred for other obesity intervention		
Referred to Tier 4 for bariatric surgery	104	Binary indicator of 1 if participant was referred to Tier 4 for bariatric surgery over 104 week period, 0 otherwise
Treatment satisfaction		
Treatment	Satisfaction	Questionnaire for Medication (TSQM)
	52, 104	Change from baseline in TSQM scale score. Scored as per version II (detailed in Appendix B on vhe.066.fm (iqvia.com)).
Safety/adverse events		
Gastrointestinal symptoms	52, 104	Binary indicator of 1 if participant experienced any nausea or vomiting in study up until the time point of interest (captured in the expected AEs), 0 otherwise

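### Home-machine blood pressure from participants with known hypertension can enter the SAP's change from clinic baseline with no separation by setting, so the descriptive within-arm BP changes may carry a device or setting offset (minor)

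*Protocol*

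**What the plan says.** **Baseline.** Protocol 8.3.1 has BP taken at the Baseline Visit under a common procedure: "Weight, waist circumference, blood pressure and pulse rate will be recorded for all the patients in line with study SOPs". Section 8.3.2 uses the same approach for weeks 52 and 104 at the study site and describes no remote variant.

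**Remote visits.** Protocol 8.10 opens its list of suspended items by saying that "the following procedures will not be performed during the COVID19 pandemic", and BP and pulse head that list. The same item then says that participants known to have hypertension "have home BP monitoring machines and their BP measurements are being collected and assessed by the study team during remote visits". For the rest, the text gives only a reason for not measuring: "There is no undue risk for those who do not have hypertension". The amendment history agrees that BP is lost for those without a home monitor. A footnote to Appendix 3 says of the suspended items: "These activities will not be completed during the COVID19 pandemic restriction period". Once restrictions end, "virtual consultations will still be an option for study visits, as preferred by the participant or recommended by the study clinician".

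**Method.** For home weight, 8.10 provides study scales, a working instruction, and either a witness or a photograph. For home BP it gives no device, cuff, number of readings or source-data rule.

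**Analysis.** SAP 2.2.1 defines systolic change as "Follow-up systolic blood pressure – baseline systolic blood pressure", with diastolic in the same form, and footnotes both as safety outcomes too. The hypertension indicator is 1 for anyone on antihypertensive medication or with systolic BP above 140 mmHg. SAP 5.5.1 restricts BP to description by arm, without a test. SAP 5.5.3 plans no sensitivity analysis. The SAP adapts week-52 weight (1.3) and the adherence definition (2.2.1) to the pandemic, but says nothing about BP setting there or in 5.8 (changes to the planned analysis).

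**The concern.** A change score is clean only if both readings come from the same measurement process. Here the first is a clinic reading under study procedures, and the second may come from a participant's own machine at home. Applied as written, the SAP formula subtracts one from the other, and any systematic home-minus-clinic difference goes into the mean change reported for the arm. BP is summarised without a model, so the raw change is the result that readers will see, in a table that serves both efficacy and safety.

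The second problem is who contributes. Remote BP exists only for participants with known hypertension, so follow-up means taken from available values combine clinic readings from everyone seen face to face with home readings from a selected subgroup. The composition of the change set therefore depends on visit mode as well as on dropout.

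**Working it through.** The plan states no figure on this point, so there is none to reproduce. The calculation shows how large the effect could be.

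**Inputs**
- Recruitment end 29/02/2020 and pandemic amendment issued 19/05/2020: protocol amendment history.
- Accrual period: assumed uniform over 24 to 30 months (730 to 913 days). Protocol 7.1 gives up to 24 months.
- Visits due from 19/05/2020: assumed all remote. This is a ceiling, because 8.10 lets face-to-face visits continue.
- Fraction of participants with known hypertension, h: assumed 0.5.
- Size of the home-minus-clinic offset, d: assumed 2 to 8 mmHg. The documents give no value or direction.

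**Step 1: share of visits due in the remote period, s.** A week-52 visit due on 19/05/2020 belongs to someone randomised 364 days earlier, on 21/05/2019, which is 284 days before recruitment closed. A week-104 visit goes back 728 days, to 22/05/2018, which is 648 days before closure.
- Week 52: 284/913 = 31% to 284/730 = 39%.
- Week 104: 648/913 = 71% to 648/730 = 89%.

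**Step 2: share of home readings among available BP values.** Participants without hypertension give no remote reading, so the denominator is clinic readings plus hypertensive home readings: share = s·h / (1 − s + s·h).
- Week 52: 0.155/0.845 = 18% to 0.195/0.805 = 24%.
- Week 104: 0.355/0.645 = 55% to 0.445/0.555 = 80%.

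**Step 3: spurious within-arm mean change = share × d.**
- Week 52: 0.18 × 2 = 0.4 to 0.24 × 8 = 1.9 mmHg.
- Week 104: 0.55 × 2 = 1.1 to 0.80 × 8 = 6.4 mmHg.

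**Sensitivity to the assumptions.** With h = 1, the home share equals s, and the ranges rise to 0.6–3.1 and 1.4–7.1 mmHg. If only half of the due visits were remote, s halves. With h = 0.5 the week-52 share is then 0.0775/0.9225 = 8% to 0.0975/0.9025 = 11%, and the week-104 share is 0.1775/0.8225 = 22% to 0.2225/0.7775 = 29%. The shifts fall to about 0.2–0.9 and 0.4–2.3 mmHg.

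**Step 4: between arms.** With a common offset, the shift in the contrast is (home share in intervention − home share in control) × d. For d = 5 mmHg:
- 50% home in both arms: each arm moves by 2.5 mmHg and the contrast by 0.
- 50% against 30%: the arms move by 2.5 and 1.5 mmHg and the contrast by 1.0 mmHg.

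These shares are illustrations only; the documents give no remote share by arm.

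**Step 5: hypertension indicator.** A participant on antihypertensives is coded 1 whatever the reading. Setting can change the code only for participants off medication, and remotely only for those among them with known hypertension.

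**The case against.** The strongest reply is that 8.10 and Appendix 3 present BP as suspended, and that home readings appear there as part of a safety justification. On that reading they may never have been meant for the endpoint. The SAP does not say that home and clinic readings are equivalent; it is silent. BP is descriptive, both arms stand side by side in Table 16.11, and equal remote shares with equal offsets cancel in the comparison.

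Most of this stands and limits the point. It does not remove it. The readings are being collected, the SAP contains no rule to exclude them, and a formula applied without such a rule will use them.

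Three stronger readings are tempting, and the documents do not support them.
- *Waist.* A reader might infer that waist is also self-measured at home and then formally tested, because it is absent from the suspended list in 8.10 and SAP 5.5.1 models it. No home waist reading is documented, and a missing value is equally consistent with the text.
- *Hypertension prevalence.* With an assumed mean of 135 and SD of 15 mmHg, a device reading 5 mmHg lower moves the share of readings above 140 from 37% to 25%. That is not a shift in the reported indicator, because treated participants stay coded 1.
- *Bias in the treatment comparison.* Differential remote use is possible in an open-label trial in which drug supply requires a virtual consultation, but no difference between arms is shown.

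**Conclusion.** The point holds in a limited form and is minor. The SAP's BP change derivations and its single systolic cut-off take no account of setting, while the protocol has home readings collected from one subgroup by an unstated method. The descriptive within-arm BP changes can therefore combine a device or setting offset with real change, and remote contributors are selected by hypertension status.

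On the stated assumptions the offset adds about 0.4 to 1.9 mmHg at week 52 and 1.1 to 6.4 mmHg at week 104. Accrual pattern, remote share, hypertensive fraction and offset are all assumed, so these figures show a possible scale and are not estimates. Any effect on the between-arm contrast is conditional and undemonstrated. The hypertension indicator is exposed only among participants off antihypertensives. The primary outcome is unaffected.

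**What to change.** Change the SAP only.
- In 2.2.1, state whether home readings enter the BP endpoints, and classify each follow-up BP as clinic or home from the visit record.
- In Table 16.11, give the number of readings by setting and arm, and show systolic and diastolic change for clinic readings only beside all readings.
- Do the same for the systolic part of the hypertension indicator, whose rows are in Table 16.10.

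Showing both rows is better than a clinic-only main result, which could discard most week-104 values and remove the hypertensive participants seen remotely.

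The cost is some wording, a derived visit-mode flag and extra table rows; the clinic-only rows will hold fewer values. The flag is not guaranteed to be in the database, since 2.2.1 notes that another planned variable was never captured. If it cannot be derived for some readings, count those as setting unknown, by arm.

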9. TREATMENT OF TRIAL PARTICIPANTS

9.1 Description of Study Treatment & Pharmacy Process

Novo Nordisk will be supplying the LIRA 3mg which will be handled according to their in-house protocols and standard operating procedures. Study drug will be managed in accordance with the requirements of all applicable regulatory guidelines.

LIRA 3mg will be provided to subjects as Saxenda® (manufacturer: Novo Nordisk).

Delivery is to be via a subcutaneous injection. LIRA 3mg has been licensed across the European Union via the EMA, for treatment of obesity for patients with and without diabetes (February 2015, Procedure No EMEA/H/C/003780/0000, Marketing ID: EU/1/15/992/001-003) and was launched within the UK in January 2017. Patients in the LIRA 3mg group (i.e., the targeted prescribing pathway/intervention group) will titrate the drug dose and will stop the medication according to the pre-specified protocol.

All study medication dosage will not exceed the stated recommendations of local guidelines and the British National Formulary. All contra-indications will be checked as part the eligibility criteria.

Study medication may be suspended or stopped by the study team if they become aware of the participant undergoing any contra-indicated procedure for out-of-study clinical care. This will be documented in the participant's study and medical notes and a decision on any potential withdrawal from the study on this basis will reside with the PI of each site. Recommencing of the study drug will follow individual safety assessments in-line with the procedure in question.

